1.0 Project Summary/Abstract

This program of research focuses on identifying neurologic biomarkers of smoking behavior in order to develop individualized smoking cessation aids. The research team has carefully designed the study protocol to ensure participant safety and confidentiality. This research will include administration of intranasal insulin and a placebo comparator. The intranasal insulin administered is an investigational drug and has been granted IND status by the FDA (IND#129432). During the times of drug effects, we will evaluate a biomarker using non-invasive equipment. Researchers are trained to be vigilant in identifying any side effects associated with the study drug and associated procedures. Anticipated risks of study drugs and equipment have been recognized by the research team and will be discussed as part of the informed consent process. Access to data collection and sensitive patient information will be limited to the Principal Investigator and designated research team. Researchers have quality control metrics in place to assure collection of accurate data, proper documentation of study activities, and predeveloped contingency plans in the event unanticipated problems occur.

Schemas are welcomed and often provide a nice visual reference for the project: The proposed work is a 2-session crossover design study intended to evaluate the effects of intranasal insulin vs placebo in smokers and non-smokers. Study participants will be randomized to either receive Treatment A (intranasal insulin) or Treatment B (placebo) during each session (Figure 1). The washout period will be 1 week in duration. Study participants will consist of healthy smokers and healthy non-smokers. Period 1 represents the first testing session and Period 2 represents the second testing session. As discussed in the above-section, one specific treatment will be administered per session.

2.0 Background/Scientific Rationale

Describe the research problem and provide rationale for the research: Although there are several FDA-approved treatments for smoking cessation, only 6% of an estimated 40 million smokers successfully quit. Taking a more patient-specific approach to resolving this healthcare concern may lead to more efficacious outcomes. The purpose of finding a biomarker is to enhance future drug development of new smoking cessation pharmacotherapeutic agents. In addition to characterizing the biomarker, we will test whether intranasal insulin – an investigational drug – can improve go/no-go accuracy in smokers.

Briefly summarize prior experience and/or history relevant to the research: The rationale for using intranasal insulin is its efficacy in relieving cognitive deficits as reviewed in several papers (Shemesh et. al., 2012, de la Monte 2013, Ott et. al., 2012, Reger and Craft 2006, Strachan 2005, Fehm 2000).

It is hypothesized that intranasal insulin will relieve cognitive dysfunction in smokers as shown in previous studies (Franken et al., 2010; Luijten et al., 2011b).

Identify any investigational agents, drugs, devices, or biologics that will be administered or implanted into subjects: For this research study, smokers and non-smokers will be administered intranasal insulin (Novolin R, 60 IU) and placebo. Placebo will consist of sterile water with 14% NaCl. During administration of either intranasal insulin or placebo, participants will receive 1 spray in each nostril every 3 minutes for a total of 6 sprays. AeroPump delivers 0.1 ml of liquid per spray. Since the concentration of insulin in Novolin R is 100 IU/mL, six sprays will deliver the 60 IU dose.

Summarize relevant preclinical data: See “Briefly summarize prior experience and/or history relevant to the research” (above).

Summarize relevant clinical data to date: The clinical benefits of intranasal insulin administration have been elucidated in the context of cognitive dysfunction alleviation (Shemesh et. al., 2012). Accumulating evidence demonstrates that conditions such as diabetes and Alzheimer’s disease are associated with a deficiency of insulin signaling to the brain, resulting in cognitive impairment and decline. Such cognitive effects could be reversed or slowed with medical intervention to efficiently deliver insulin to the brain. Intranasal insulin administration is a noninvasive and efficient way to bypass the blood-brain barrier; thus, it may be a useful way to reintroduce insulin to the central nervous system to alleviate cognitive dysfunction caused by a hormonal deficit.

Intranasally administered insulin has previously been shown to directly elicit changes in cognitive function with little impact on blood glucose levels (Kern et al., 1999). When insulin was administered intranasally to a cohort of healthy, euglycemic men, the dose administered was not significantly detectable from placebo by a change in blood glucose levels or cardiovascular activity. However, the treatment caused a significant reduction in the baseline-to-peak amplitude of the N1 and P3 AEP components as well as an increase in P3 latency. These results indicate that intranasal insulin administration bypasses the bloodstream to directly impact the central nervous system.

Intranasal insulin may also be a useful smoking cessation treatment, due to exploratory studies of its effects on craving in smokers (Hamidovic et al. 2017). Administration of intranasal insulin resulted in a lower self-reported urge to smoke and restored the cortisol response to experimentally induced stress. These results indicate that intranasal insulin may be an effective and viable smoking cessation product.

Provide a rationale for the dosing or use of the device, risks to subjects, and potential benefits to subjects: We conducted two clinical trials with intranasal insulin (Hamidovic et al., 2017). The 60 IU dose is identical as in those two studies (IND #116626 and IND# 120700). The first study (IND #116626), was a parallel-design clinical trial involving one-time administration of intranasal insulin (60 IU) to smokers who were abstinent from smoking overnight. The second study (IND# 120700) was a 36-hour crossover, inpatient hospital study in which smokers received two administrations of intranasal insulin (60 IU) on two separate days. None of the subjects in either of the two studies experienced hypoglycemia. Circulating glucose was not lower for the insulin group in comparison to the placebo group in either study. Olfactory function (measured with Sniffin’ Sticks (US Neurologics)) was no different between the insulin and placebo groups in both studies. Sniffin’ Sticks involves presentation of 12 different pens containing different smells. After the presentation of each pen,

participants complete a multiple-choice question with 4 possible choices; one of which is the answer corresponding to the correct smell. Local irritation was higher in the intranasal insulin group in comparison to the placebo group. Table 1 lists results of the Sniffin' Sticks test, which measures the ability to correctly identify various smells. Table 2 lists the all the events reported in the study by treatment group in the IND#120700 study.

Table 1. Summary of Sniffin' Sticks (US Neurologics) Scores throughout the Study by Treatment for IND#120700

Appointment	Treatment	Mean	Std. Dev.
Screening	NA	11	0.80
Session 1 (day 1)	Insulin	11.29	0.70
Session 1 (day 2)	Insulin	11.36	0.61
Session 2 (day 1)	Insulin	10.9	0.87
Session 2 (day 2)	Insulin	11.1	0.78
Session 1 (day 1)	Placebo	10	0.66
Session 1 (day 2)	Placebo	11.18	0.83
Session 2 (day 1)	Placebo	11.40	0.66
Session 2 (day 2)	Placebo	11.30	0.64
Follow-up	Both	11.25	0.77

Table 2. Adverse events reported by study participants.

Event	Number of occurrences during placebo treatment	Number of occurrences during insulin treatment	Number of occurrences reported at follow-up
Nasal occurrences			
Rhinorrhea	1	1	
Irritation	5	7	
Other			
Dizziness		1	
Sweating		2	
Headache		1	
Nonspecific pain			2
Visual disturbances			1
Confusion	1	2	
Tingling (mouth)		1	
Shaking		1	1
Anxiety	1	1	
Diarrhea			1
Restless		1	
Uncomfortable		1	
Watering eyes		2	
Menorrhagia			1

Given the growing evidence that intranasal insulin prevents neuronal damage, reduces nicotine cravings (Hamidovic et al., 2017) and improves cognition in diabetes, stroke, postoperative cognitive dysfunction, developmental delay, Parkinson's disease, bipolar disorder, Alzheimer's disease and HIV-associated neurocognitive disorders (summarized in Nedelcovych et al., 2018), a recent study compared insulin exposure in mouse brain and plasma following intranasal and subcutaneous administration of 2.4 IU (Nedelcovych et al., 2018). Whereas the subcutaneous insulin achieved therapeutically relevant concentrations in the brain ($AUC_{brain} = 2537 \text{ h}\cdot\mu\text{IU/mL}$), it dramatically increased plasma insulin ($AUC_{plasma} = 520\,351 \text{ h}\cdot\mu\text{IU/mL}$), resulting in severe hypoglycemia and in some cases death. The intranasal administration of the same dose resulted in similar insulin levels in the brain ($AUC_{brain} = 3442 \text{ h}\cdot\mu\text{IU/mL}$) but substantially lower plasma concentrations ($AUC_{plasma} = 354 \text{ h}\cdot\mu\text{IU/mL}$), amounting to a ~2000-fold increase in the AUC_{brain} :plasma ratio relative to SC. The intranasal dosing also had no significant effect on blood glucose. Intranasal insulin administration over 9 days increased brain glucose and energy metabolite concentrations (e.g., adenosine triphosphate and phosphocreatine) without causing overt toxicity, suggesting that intranasal insulin may be a safe therapeutic option.

Based on the 60-kg human, the 2.4 IU/kg dose given in the Nedelcovych et al (2018) study converts to a 144 IU dose, which is above the 60 IU dose we plan to administer as a one-time dose in the proposed study.

3.0 Objectives/Aims

Identify hypotheses being tested/primary endpoints/primary purpose of the protocol: The aim of the proposed work is to evaluate go/no-go accuracy as a neurologic biomarker of smoking behavior. Our hypothesis is that following intranasal insulin administration, smokers will have an improved go/no-go accuracy.

Study duration: This duration of the research study is 2 years starting January 2018 – January 2020.

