6.0 Study Design and Procedures

List any collaborating sites where human subjects research will be performed, and describe the role of those sites and collaborating investigators in performing the proposed research (if applicable): This study will be only conducted at University of Illinois. Study space will be rented at Center for Clinical and Translational Science. In addition, UIC nurse will be responsible for performing nasal examination and collecting blood samples. Study personnel – working out of the PI's laboratory - will ensure regulatory compliance, recruit participants, as well as collect and analyze the data. The PI's lab is located on the first floor of UIC College of Pharmacy. Study materials, equipment and all paper copies will be locked in the office of research staff affiliated with the study.

Describe the study design. The description should be capable of meeting the study objectives: This is a two group, two session study. The only eligibility criteria separating the two groups is the smoking status, otherwise the study population will consist of healthy volunteers. Following successful completion of the "Initial Survey", study participants will be scheduled for a 3-hr In-Person Screening visit. At the in-person screening, participants will 1. be consented, 2. provide urine and breath samples, 3. complete surveys, and 4. receive study instructions. After the completion of the "In-Person Screening", study participants will be scheduled for two study sessions, separated by a minimum of 1 week. During the study session, in random order, study participants will receive either intranasal insulin (60 IU) or placebo. This is a cross-over study –participants receiving intranasal insulin will receive placebo next, and vice-versa. Please refer to Table 1 for a summary of the study

session. The sessions will be identical, other than participants receiving intranasal insulin or placebo in random order.

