6.1 Procedures and Assessments

Provide a thorough description of all study procedures, assessments and subject activities in a logical and sequential format. Indicate what study activities happen when and where, including, when applicable, a study schedule that notes number and length of study visits for subjects.

Table 3. Outline of Study Session	
TIME	PROCEDURE
8:00-8:30	Determination of session eligibility (urine and breath tests)
8:30-8:50	Nicotine gum break (smokers), generic chewing gum break (non-smokers)
8:50-9:00	Nicotine blood sample
9:00-9:05	POC glucose check
9:05-9:15	Nares exam
9:15-10:00	Relaxation phase (both smokers and non-smokers)
10:00-10:06	Spray administration
10:10-10:30	Equipment setup
10:30-11:40	Go-No/Go task
11:40-11:45	Olfactory function test
11:45-12:00	Discharge procedure (POC measurement)

Study session will begin at 8:00 AM. First, the research coordinator will ensure that the lab has a signed consent form on file from the participant. Smokers will be instructed to smoke the normal amount of cigarettes they usually smoke upon waking prior to each session, then refrain from smoking until the end of the session. For example, if they usually smoke 2 cigarettes upon waking, they will be instructed to smoke 2 cigarettes prior to the first session (30 minutes upon waking) and 2 cigarettes prior to the second session (30 minutes upon waking). Participants will be asked if they have had breakfast. If they did not eat breakfast that morning, research coordinator will give them a granola bar and re-emphasize the importance of eating breakfast. Next, from 8:00 AM to 8:30 AM, urine and breath samples will be obtained by the study coordinator, for verification of absence of alcohol intake. A urine sample will be obtained to rule out illicit drug intake and pregnancy. See Section 6.2 Specimen Considerations for more information on urine sample collection and analysis protocol.

At 8:30, smokers will take a 20-minute nicotine chewing gum (Nicorette gum, 4mg) break, and non-smokers will take a 20-minute generic, non-nicotine chewing gum break. As per the instructions given by Nicorette, smokers will be instructed chew the gum slowly until they experience a tingling sensation, then to place the gum between their cheek and gum until the tingle subsides and repeat until most of the tingle is undetectable. Non-smokers will be instructed to chew the generic gum at their own pace.

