12.0 Statistical Considerations

If a study incorporates qualitative rather than quantitative methods, indicate this and describe qualitative analysis and disregard the rest of this section: This study does not incorporate qualitative data analysis.

Describe how the data will be examined and statistically analyzed to answer the objectives: Go/no-go accuracy will be evaluated in a 2 x 2 repeated measure ANOVA, with group, treatment and treatment x group interaction entered into the model.

Provide a brief sample size calculation or description of sample size calculation. Include methods and assumptions such as loss to follow-up, as appropriate: Effect size is estimated from Luijten et al (2011). In that study, effect size was 0.24.

We anticipate 120 participants completing the study. An a priori power analysis was conducted using G*power 3.1.9.2 for an ANOVA test, repeated measures and within-between interaction. With 2

within and 2 between factors; a base correlation=0.6; power=0.95; alpha=0.05, the total of 120 participants (60 per group) is required to capture an interaction between group and treatment on ERN.

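### Section 12.0 names no contrast for the biomarker aim; the group main effect, if used for it, would understate the insulin-free difference when insulin helps smokers more than non-smokers

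*Combined protocol and SAP*

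**What the plan says.** The documents raise two questions. Section 1.0 begins: "This program of research focuses on identifying neurologic biomarkers of smoking behavior in order to develop individualized smoking cessation aids". Section 2.0 separates the biomarker from the drug test with "In addition to characterizing the biomarker, we will test whether intranasal insulin", and goes on to ask whether insulin can raise accuracy in smokers. Section 3.0 states the aim, "The aim of the proposed work is to evaluate go/no-go accuracy as a neurologic biomarker of smoking behavior", followed by one hypothesis, which concerns the drug: "Our hypothesis is that following intranasal insulin administration, smokers will have an improved go/no-go accuracy". It states no hypothesis about a difference between smokers and non-smokers.

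The analysis in Section 12.0 is a "2 x 2 repeated measure ANOVA, with group, treatment and treatment x group interaction entered into the model". It names no simple effect, no placebo-session contrast and no period term. The only effect singled out is the group-by-treatment interaction, in the sample size paragraph, where the outcome is ERN rather than accuracy. The inputs there are "a base correlation=0.6; power=0.95; alpha=0.05", with 60 participants per group.

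On order of treatment, Section 6.0 says that "in random order, study participants will receive either intranasal insulin (60 IU) or placebo", without mentioning stratification by smoking group. Neither the screening visit (Section 6.0) nor the part of the session before the spray (Section 6.1) includes a go/no-go task. The placebo session is therefore the only insulin-free measurement of accuracy.

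**The concern.** An aim with no assigned contrast leaves the choice open until the data are seen. At least two estimates could serve: the group main effect and the placebo-session difference. They estimate the same quantity only if insulin benefits both groups equally. The main effect is the model's only direct smoker/non-smoker term, so an analyst could easily reach for it. It mixes the drug session into a comparison meant to describe smoking status. If smokers do worse on placebo and insulin helps them more, the difference comes out too small, and accuracy may look a weaker biomarker than it is. The placebo-session difference avoids this but is exposed to period effects, for which the model has no term.

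**Working it through.** **The plan's own figure.** The stated total of 120 does not reproduce. With the default G*Power formula, lambda = f² x N x 2/(1 - rho), f = 0.24 and rho = 0.6, the N for 95% power is 48, and power at 120 is 0.9999. N = 120 corresponds to f of about 0.148. That is a separate issue. What follows uses only 60 per group and correlation 0.6 from Section 12.0.

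**Assumed inputs.** The session SD is set to 1. D is the placebo-session mean of non-smokers minus smokers. I is the insulin benefit in smokers minus that in non-smokers, and r = I/D. The documents give neither D nor r for accuracy.

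**What the main effect estimates.** The group difference is D on placebo and D - I on insulin. Its average is D - I/2 = D(1 - r/2). The understatement is 0%, 12.5%, 25% and 50% at r = 0, 0.25, 0.5 and 1. A simulation of 20,000 trials with D = I = 0.5 SD gave a group term of 0.250 and a placebo-session difference of 0.500.

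**Precision.**
- Placebo contrast: variance 2/60 = 0.0333.
- Two-session mean: variance ((1 + rho)/2) x 2/60 = 0.8 x 0.0333 = 0.0267 at rho = 0.6. The placebo contrast has 1/0.8 = 1.25 times this variance.
- The two have equal power at r = 2(1 - sqrt((1 + rho)/2)), which is 0.33, 0.21 and 0.10 at rho = 0.4, 0.6 and 0.8. Below that r the main effect has more power.

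**Power of the placebo contrast** (F test on 1 and 118 df, alpha 0.05). 80% power needs lambda = 7.98, so D = sqrt(7.98 x 2/60) = 0.516 SD. 95% power needs lambda = 13.21, so D = 0.66 SD.

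**Illustration at D = 0.516, rho = 0.6.** The main effect has lambda = D²(1 - r/2)²/0.0267. The interaction has lambda = (rD)²/(4(1 - rho)/60) = (rD)²/0.0267.

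| r | Main effect power | Interaction power | Placebo contrast power |
|---|---|---|---|
| 0 | 0.88 | – | 0.80 |
| 0.25 | 0.78 | 0.12 | 0.80 |
| 0.5 | 0.65 | 0.35 | 0.80 |
| 0.75 | 0.50 | 0.65 | 0.80 |
| 1 | 0.35 | 0.88 | 0.80 |

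**Other values of D** (rho = 0.6). At 0.4 SD the placebo contrast has 58% power, against 68%, 45% and 23% for the main effect at r = 0, 0.5 and 1. At 0.6 SD it has 90%, against 95%, 78% and 45%.

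**Would the interaction test give warning?** At r = 0.5 and D = 0.516, lambda is 1.66, 2.49 and 4.99 at rho = 0.4, 0.6 and 0.8. Power is 0.25, 0.35 and 0.60, so the test is non-significant in about 75%, 65% and 40% of trials. At the interaction size with 95% power for rho = 0.6, sqrt(13.21 x 0.0267) = 0.59 SD (r about 1.15), main-effect power falls to about 26%, but the interaction is flagged in 95% of trials.

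**Period.** Each person contributes one session to each period, so a period effect common to both groups cancels in the two-session mean. In the placebo contrast it leaves a shift equal to the period effect times the difference between groups in the order split. With an assumed 0.3 SD period effect and orders split 36/24 in one group and 24/36 in the other, the shift is 0.3 x 0.20 = 0.06 SD, or 12% of D. This is a tail case: under simple randomisation the SD of the split difference is sqrt(2 x 0.25/60) = 0.091, so 0.20 is about 2.2 SDs (probability about 3%). In 20,000 simulated trials of that case at r = 0.5, the contrast averaged 0.885D (power 0.69) without a period term and 1.00D (power 0.80) with one. The term costs 0.8% more variance under that split and nothing under balance.

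**The case against.** Three arguments have force.

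First, a reader might infer that the plan tests the biomarker aim with the group main effect and so builds in a bias. The documents do not say that: Section 12.0 lists the term without giving it a role. The documentable gap is the missing contrast, and the attenuation depends on an analysis choice the plan never states.

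Second, the biomarker aim could be read as one of drug response, since Section 3.0 follows it only with an insulin hypothesis and Sections 1.0 and 2.0 link biomarkers to developing cessation treatments. The treatment and interaction terms would then serve it. The wording of Section 2.0 favours two separate questions, but nowhere is characterising the biomarker defined as a placebo-session difference. This ambiguity is itself a reason to name the contrast.

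Third, shrinkage needs a deficit in smokers on placebo and a larger benefit in smokers. The hypothesis asserts improvement in smokers but not that it exceeds any in non-smokers. The sample size text looks for an interaction, but on ERN. With equal benefit, or r below about 0.21 at correlation 0.6, the main effect is the more powerful choice. A large differential effect would usually show in the interaction.

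It would also be wrong to infer that the trial cannot answer the question: the placebo-session difference is available from the data already planned.

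**Conclusion.** The point holds in a limited form. No contrast is prespecified for the biomarker aim, and the planned crossover model has no period term. The relation D(1 - r/2) is exact for the usual ANOVA main effect. It implies understatement only if smokers do worse on placebo and insulin helps them more than non-smokers. All power figures rest on assumed D and r and are illustrations; D = 0.516 SD was chosen because it gives the placebo contrast 80% power. How often the interaction would miss the problem depends strongly on the correlation. The 0.06 SD period shift is an unlikely case, not an expected one.

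The stated 95% power belongs to the interaction and does not carry over to the placebo contrast. The change is worth making before analysis because it removes an open choice cheaply. The documents do not support saying that the planned analysis is biased for its aim.

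**What to change.** Amend Section 12.0 as follows.

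1. Add a period term (session 1 or 2) to the group-by-treatment model, fitted as a mixed model with separate variances for the two sessions and their covariance.
2. Name smokers minus non-smokers in the placebo session as the contrast for the biomarker aim, reported whatever the interaction shows. Treat the group main effect as descriptive.
3. Rank this contrast against the insulin hypothesis, for example as secondary to it, so that multiplicity is settled in advance. State that the 95% power does not apply to it and that 60 per group gives 80% power for about 0.52 SD.
4. State as a limitation that the placebo session is insulin-free but not free of acute nicotine differences. Section 6.1 says "Smokers will be instructed to smoke the normal amount of cigarettes they usually smoke upon waking prior to each session", and only smokers receive nicotine gum before the task, in both sessions. The contrast therefore mixes smoking status with recent nicotine.

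This needs no new data. It costs 25% more variance than the two-session mean at correlation 0.6 (power 80% against 88% at r = 0 for D = 0.516 SD), hence less power when r is below about 0.21 (0.33 at correlation 0.4, 0.10 at 0.8). A single period term also assumes that practice effects are the same in both groups, which should be stated.
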